## 9.2 Data Collection

Data collection requirements are summarized in Table 2 below.

**Medtronic Business Restricted**

**Table 2: Data Collection Requirements for Enrolled Subjects**

Category	Sub-Category	PIC Signed	Required eCRFs													
			Consent	Inclusion/ Exclusion	Baseline	Medical History	Procedure	Secondary Procedure	Subject Visits	Dialysis Treatment Record	Vascular Access Questionnaire	Cannulator Satisfaction Survey	Dialysis Catheter Use	AE	Device Deficiency	Study Exit
Enrolled 	Safety Population 	X	X	X	X	X	X	X	X	X	X	X	X	X 	X 	X
	Access Failure 	X	X	X	X	X	X 							X 		X
	Device Failure 	X	X	X	X	X	X							X 	X 	X
	Procedure Failure 	X	X	X	X	X	X							X 	X 	X

**Enrolled:** subject who signed and dated the informed consent form.

**Safety population:** enrolled subjects for whom the procedure is attempted, and the Ellipsys System is deployed.

As applicable

**Access failure:** enrolled subjects in whom the Ellipsys device is not deployed due to 1) the needle or wire cannot be introduced, or 2) vessel spasm precludes continuing the procedure. These subjects may be re-scheduled for another attempt at access later the same day or within 30 days. If no second attempt is made or the second attempt is not successful, these subjects will be considered access failures and will be followed for safety through clinic discharge. Two Procedure eCRFs are to be completed for subjects in this category. If an AE occurs prior to discharge, subject will be followed for safety until resolution.

**Device failure:** a malfunction of the Ellipsys System during use that precludes creation of a percutaneous AV fistula. A second Catheter may be deployed, or a second Controller may be used to complete the procedure. A Device Deficiency eCRF must be completed to report the device failure.

**Procedure failure:** the Ellipsys System is deployed and functions per specification, however, the AV fistula creation is unsuccessful due to incorrect placement in the patient anatomy. If this is observed immediately after deployment and the introducer sheath or guidewire is still in place, a second deployment may be attempted to complete the procedure.

## 9.3 Scheduled Follow-up Visit Windows

After receiving notice of successful device application, Medtronic will provide the target dates and windows for each visit to the study site if applicable. Should a subject miss a visit or the visit fall outside the pre-specified window, a protocol deviation must be reported, and the original follow-up schedule maintained for subsequent visits.

Data analyses include follow-up visits, regardless of whether the visit occurs within the window.

Therefore, a late visit is preferred over a missed visit but must be accompanied by a protocol deviation.

Follow-up visit windows are listed in Table 3 and are based on days post-AVF creation.

**Table 3: Study Follow-Up Visit Windows**

Study Follow-up Visit	Window (Calculated days post-AVF creation procedure)
-----------------------	---

**Medtronic Business Restricted**

**CONFIDENTIAL**

056-F275 Rev E Clinical Investigation Plan Template

	Window Start (days post-procedure)	Target (days post-procedure)	Window End (days post-procedure)
1 Week (± 2 days)	Day 5	Day 7	Day 9
4 Weeks (± 7 days)	Day 23	Day 30	Day 37
3 Months (± 14 days)	Day 76	Day 90	Day 104
6 Months (± 30 days)	Day 150	Day 180	Day 210
12 Months (+ 60 days)	Day 360	Day 360	Day 420

## 9.4 Subject Screening

Patient eligibility for a surgical or percutaneous AVF will be assessed based on standard of care institutional guidelines which may include medical history, physical examination, blood pressure, ultrasound vascular mapping and other parameters. Those patients who are eligible for a surgical or percutaneous AVF may be considered for inclusion in this study. Patients who meet all general screening criteria will be asked to participate in the study. Patients who fail to meet one or more of the I/E criteria will be considered screening failures. If the patient agrees to participate, a personally signed and dated informed consent will be obtained. These subjects may then proceed with study specific screening procedures, including the pre-procedure confirmatory vascular mapping by ultrasound.

Institutional screening procedures may be used to fulfill study criteria if the investigator assesses that the subject's condition has remained stable. Female subjects will be assessed by history and/or review of medical records for reproductive potential and if necessary, a pregnancy test will be done to exclude pregnancy. Subjects who sign and date the informed consent form will be enrolled in the study and proceed with the study procedure.

## 9.5 Subject Consent

Informed consent is defined as a legally effective documented confirmation of a subject's or their legally authorized/designated representative voluntary agreement to participate in a particular study after information has been given and explained to the subject on all aspects of the study that are relevant to the subject's decision to participate. This process includes obtaining an informed consent (IC) Form that has been approved by the study site's IRB and signed and dated by the subject or their legally authorized/designated representative. A subject may only consent after information has been given and explained to the subject on all aspects of the clinical investigation that are relevant to the subject's decision to participate.

Prior to enrolling subjects, the IC Form must be approved by the IRB. The document(s) must be controlled (i.e. versioned and/or dated) to ensure it is clear which version(s) were approved by the IRB. Any adaptation of the sample IC Form must be reviewed and approved by Medtronic and the IRB reviewing the application prior to enrolling subjects. The sample IC Form is available separate from this CIP.

The investigator must notify the subject or their legally-authorized/designated representative of any significant new findings about the study that become available during the course of the study which are pertinent to the safety and well-being of the subject, as this could impact a subject's willingness to participate in the study. If relevant, consent may be requested from subjects to confirm their continued participation.

Prior to initiation of any study-specific procedures, IC must be obtained from the subject or their legally authorized/designated representative. Some general inclusion/exclusion criteria that are standard of care may be evaluated prior to the subject signing the IC Form. Likewise, privacy or health information protection regulation may require subjects to sign additional forms to authorize study sites to submit subject information to the study sponsor. The IC process must be conducted by the principal investigator or an authorized designee, and the IC Form must be given to the subject or their legally authorized/designated representative in a language he/she is able to read and understand. The process of IC must be conducted without using coercion or undue improper influence on or inducement of the subject to participate by the investigator or other study site personnel. The IC process shall not waive or appear to waive subject's legal right. The language used shall be as non-technical as possible and must be understandable to the subject and the impartial witness, where applicable.

The subject must have ample time and opportunity to read and understand the IC form, to inquire about details of the study, and to decide whether or not to participate in the study. All questions about the study should be answered to the satisfaction of the subject.

When the subject decides to participate in the study, the IC Form must be signed and personally dated by the subject and investigator or authorized designee, as required by the IRB.

A copy of the IC Form, signed and dated, must be provided to the subject and his/her authorized designee.

If the IC is obtained the same day the subject begins participating in study-related procedures, it must be documented in the subject's case history that consent was obtained prior to participation in any study-related procedures. It is best practice for the IC process to be documented in the subject's case history, regardless of circumstance.

In the event the subject cannot read and/or write, witnessed (impartial witness) IC will be allowed, provided detailed documentation of the process is recorded in the subject's case history and the witness signs and dates the IC. The IC should document the method used for communication with the prospective subject and the specific means by which the prospective subject communicated consent to participate in the study.

The original of the signed IC Form must be filed in the hospital/clinical chart and/or with the subject's study documents.

The IC must be available for monitoring and auditing.

## 9.6 Enrollment

A subject is considered enrolled when the consent process has been finalized and the IC Form has been signed and dated. The date the subject or the subject's authorized/designated representative signed the IC and Data Protection Authorization, as required by law, must be documented in the subject's medical records. A log of all subjects enrolled in the study should be maintained. Enrollment can be a stand-

alone visit or can occur on the same day as the baseline visit. Once consent is obtained, report adverse events/deaths, study deviations and subject exits as they occur.

## 9.7 Baseline

The baseline visit can be a stand-alone visit or can be performed on the same day prior to the AVF creation procedure.

The following information is required to be collected at the baseline visit:

- Demographics
- Clinical Evaluation
- Vital Signs
- Medical/Surgical History
- Medications
- Hemodialysis History
- Baseline Duplex Ultrasound (vascular mapping) is performed and assessed by the Investigator to confirm the subject meets pre-procedure inclusion criteria 10 and 11. It will not be submitted to the DUS Core Lab.
- Adverse events are required from the moment the subject is enrolled in the study (i.e. subject signed and dated the informed consent form)

## 9.8 AV Fistula Creation Procedure (Day 0)

The following information is required to be collected at the AV Fistula creation procedure (Index Procedure) visit:

- Date of procedure
- Visit type: Initial Study Procedure or Reattempt Study Procedure
- Pre-procedure Duplex Ultrasound (vascular mapping) is performed and assessed by the Investigator to confirm the subject meets pre-procedure inclusion criteria 10 and 11. It will not be submitted to the DUS Core Lab.
- Pre- and Intra-Operative Medications
- Procedure Times
- Ellipsys Catheter and Power Controller Identification
- Procedure information (including access, device deployment, fistula creation, and post-AVF balloon dilation)
- Post-procedure Duplex Ultrasound (submit to DUS Core Lab) vessel dimensions and flow rates
- Assess fistula patency at discharge
- Adverse event is required from the moment the subject is enrolled in the study (i.e. subject signed and dated the informed consent form)
- If a complication or adverse event occurs intra-procedure, the details should be captured in the Adverse Event CRF and the Device Deficiency CRF if applicable

***Medtronic Business Restricted***

- If an adjunctive procedure is required during the AVF creation procedure, the details of the procedure will be documented on the Adjunctive/Secondary Procedure CRF and will indicate that the adjunctive procedure occurred during the AVF creation procedure. Ballooning performed during the AVF creation procedure is not recorded on the Adjunctive/Secondary Procedure CRF, only on the Procedure CRF.
- Document any technical issues with the procedure

Adjunctive procedures are defined as any procedure done during the endo AVF creation procedure. These procedures will be documented on the Adjunctive/Secondary Procedure CRF. Balloon angioplasty is not considered an adjunctive procedure and details of balloon angioplasty during the endo AVF creation procedure will be captured on the Procedure CRF.

There may be cases where the Ellipsys device is not deployed due to access failure defined as 1) the needle or wire cannot be introduced, or 2) vessel spasm precludes continuing the procedure. These subjects may be re-scheduled for another attempt at access later the same day or within 30 days. If no second attempt is made or the second attempt is not successful, these will be considered access failures. These subjects will be followed for safety through clinic discharge.

Ultrasound and/or angiographic evaluation during the AVF creation procedure following AVF creation using the Ellipsys System and balloon dilation, will be used to determine the absence/presence of vessel dissection/perforation, evidence of distal emboli and possible hemorrhagic events. Post-procedure ultrasound and/or angiography will be performed and analyzed by the investigator. The post-procedure ultrasound will be submitted to the DUS Core Lab for analysis. If any secondary procedures listed in section 9.11 are required to mature or maintain the AVF or re-establish flow subsequent to completion of the AVF procedure, they will be documented in the Adjunctive/Secondary Procedure CRF and the AE CRF if applicable.

## 9.9 Recommended Antiplatelet/Anticoagulant Regimen

Based on the institutional standard of care and the judgement of the treating physician, subjects may be started or maintained on an anti-platelet or anti-coagulant regimen prior to or during the procedure and/or initial follow-up. The following measures are recommended to minimize risk of early thrombosis and/or occlusion:

1. Pre-procedure loading dose of 300 mg Plavix and 325 mg Aspirin given at index procedure
2. Intra-procedure injection of 3000 units heparin via the access sheath once radial artery access is achieved

## 9.10 Scheduled Follow-up Visits

Scheduled visits will occur at 1 Week, 4 Weeks, 3-, 6-, and 12-Months post-AVF creation. At each post-procedure follow-up visit, the subject's physical and vascular status will be assessed.

The following information is required to be collected at follow-up visits:

- Duplex Ultrasound (submit to DUS Core Lab) vessel dimensions and flow rates
- Evaluation of study AV Fistula
- Evaluation of upper extremity with access site created by study AVF
- Medications

**Medtronic Business Restricted**

**CONFIDENTIAL**

056-F275 Rev E Clinical Investigation Plan Template

- Secondary Procedures
- Hemodialysis Records
- Adverse Events
- Cannulator Satisfaction Survey (3-, 6-, and 12-month visits only), see Appendix 2: Cannulator Satisfaction Survey. If subject has not started receiving dialysis through the study AVF at the scheduled follow-up visit, the Cannulator Satisfaction Survey should not be completed
- Subject VAQ (collected at the 6-month visit only), see Appendix 1: Vascular Access Questionnaire

## 9.11 Secondary Procedures

Secondary Procedures are surgical procedures or percutaneous interventions that may be needed to mature or maintain the AVF or to re-establish flow to meet the prescribed dialysis parameters. The need for such procedures will be assessed by the Investigator subsequent to completion of the AVF procedure.

Secondary procedures do not include procedures performed during the procedure to create the study AVF, see section 9.8 for details of the AV fistula creation procedure. Secondary procedures are procedures subsequent to completion of the AVF procedure.

Additional secondary procedures can include, but are not limited to:

- Banding
- Branch Ligation
- Embolization Coils
- Embolization Plugs
- Percutaneous transluminal angioplasty (PTA)
- Stenting
- Transposition / Elevation / Superficialization
- Valvulotomy

Secondary Procedure information will be collected via the Adjunctive/Secondary Procedure CRF and an Adverse Event CRF, if applicable. If the above procedures are required during the AVF creation, they are considered adjunctive procedures, the details and timing of the procedure will be recorded on the Adjunctive/Secondary Procedure CRF, section 9.8 provides details and definition for adjunctive procedures.

## 9.12 Assessment of Efficacy

The primary effectiveness endpoint is described in section 4.1.2 as cumulative patency through 12 months post-AVF creation. Cumulative patency is defined as freedom from access abandonment from time of access creation.

## 9.13 Assessment of Safety

The primary safety endpoints are described in section 4.1.2 and are defined as follows:

***Medtronic Business Restricted***

- Early occlusion is defined as the percentage of subjects with total occlusion within 7 days of the AVF creation procedure
- Study related serious adverse event rate is defined as the rate of serious adverse events related to the device, study procedure or secondary procedure to maintain or re-establish patency through 12 months.

A full description of adverse events and reporting can be found in section 11.

## 9.14 Recording Data

Data entered into the electronic database must be traceable to source documents. Source documentation is defined as the first time data appear, and may include original documents, data, and records (e.g., hospital records, clinical and office charts, procedure reports, laboratory notes, memoranda, subjects' questionnaires or evaluation checklists, recorded data from automated instruments, and copies or transcriptions certified after verification as being accurate copies).

In general, eCRFs (or paper copies) may not serve as source documents. An exception may be the completion of QoL Questionnaires and clinical scales. Source documentation for data elements not routinely captured in medical records may vary from study site to study site; the study site may use source document worksheets if identified as source documents.

The investigator must ensure the availability of source documents from which the information on the eCRFs was derived. The type and location of source documents should be documented. Where printouts of electronic medical records, are provided as source documents, or where copies of source documents are retained as source documents, those should be certified. Certification must contain (1) the signature of the individual making the copy, (2) the date the copy was made and (3) a statement attesting to the accuracy and completeness of the copy.

The source documents must be made available for monitoring or auditing by Medtronic's representative or representatives of the competent authorities and other applicable regulatory agencies.

The CRF may be considered source for the following data collection elements:

- AE eCRF
  - Date study site became aware of event
- DD eCRF
  - Date study site became aware of event
- Subject Death
  - Date study site became aware of death
- Deviations
  - Reason for deviation

## 9.15 Deviation Handling

A study deviation is defined as an event within a study that did not occur according to the CIP or the CTA. Deviations may include, but are not limited to the following:

- Failure to obtain informed consent prior to participation
- Incorrect version of the informed consent form used

***Medtronic Business Restricted***

- Failure to obtain IRB approval before the start of enrolling subjects in the study
- Included subject did not meet inclusion/exclusion criteria
- Required testing and/or measurements not done or incorrectly done
- Subject did not attend follow-up visit
- Follow-up visit was completed outside window
- Unauthorized use of Ellipsys system outside of CIP
- Adverse events/ Adverse Device Effects or device deficiencies not reported in the required timeframe as specified in the CIP
- Source data permanently lost
- Enrollment of subjects during lapse of IRB approval
- Enrollment limits exceeded

Investigators are required, whenever possible, to obtain prior approval from Medtronic before initiating changes in or deviations from the investigational plan, except where necessary to protect the life or physical well-being of a subject in an emergency. Such approval shall be documented in writing and maintained in the study files. Prior approval is generally not expected in situations where unforeseen circumstances are beyond the Investigator's control, (e.g., subject did not attend scheduled follow-up visit), the event, however, is still considered a deviation.

In the event the deviation involves a failure to obtain a subject's consent, or is made to protect the life or physical well-being of a subject in an emergency, the deviation must be reported to the IRB as well as Medtronic as soon as possible but no later than five (5) working days from the date of the deviation occurrence.

Reporting of all deviations should comply with IRB policies and/or local laws and/or regulatory agencies and must be reported to Medtronic as soon as possible upon the site becoming aware of the deviation. Subject specific deviations shall be reported on the Protocol Deviation eCRF; all non-subject specific deviations (e.g. unauthorized use of an investigational device outside the study, unauthorized use of an investigational device by a physician who has not signed an Investigator Agreement, etc.) shall be reported to Medtronic in writing.

Medtronic is responsible for analyzing deviations, assessing their significance, and identifying any additional corrective and/or preventive actions which may include amending the CIP, conducting additional training, terminating the investigation, etc. Repetitive or serious investigator compliance issues may represent a need to initiate a corrective action plan with the investigator and site, and in some cases, necessitate suspending enrollment at that site until the problem is resolved or ultimately terminating the investigator's participation in the study. Medtronic may provide site-specific reports to investigators summarizing information on deviations that occurred at the investigational site on a periodic basis.

## 9.16 Subject Exit, Withdrawal or Discontinuation

Every subject should be encouraged to remain in the study until they have completed the required follow-up per the CIP. Subjects shall be included in the analyses up to the time that consent was withdrawn. Subjects who discontinue participation prior to study completion shall be included in the analysis of results but shall not be replaced in the inclusion of total study subjects.

***Medtronic Business Restricted***

## 9.16.1 Study Exit

A study exit eCRF is required for all subjects. Prior to exiting a subject from the study, it is recommended to follow the subject until all ongoing system and/or procedure related AEs are resolved or unresolved with no further actions planned. Following exit, subjects will continue to receive standard medical care. Subjects are urged to remain in the study as long as possible but may be exited from the study for any of the following situations:

- Study completed
- Subject lost to follow-up
- Subject death
- Subject did not meet inclusion/exclusion criteria
- Subject was not treated with the study device
- Subject did not provide consent
- Subject chooses to withdraw (e.g., consent withdrawal, relocation to another geographic location)
- Investigator deems withdrawal necessary (e.g., medically justified, inclusion/exclusion criteria not met, failure of subject to maintain adequate study compliance)

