## 9.16.5 Investigator Withdraws Subject

No subjects should be withdrawn by investigators unless compelling medical justification is present. It is recommended investigators discuss any withdrawals with the study team prior to withdrawing subjects. If an Investigator Withdrawal is necessary, the following data should be collected prior to subject withdrawal if possible:

- Reason for subject withdrawal
- Rationale and/or documented safety concern

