## 11.5 Reporting of Adverse Events

The investigator is required to assess and document in the medical record all SAEs, ADEs, SADEs, and DDs (per the definitions in Table 5) observed in subjects from the time of study enrollment. AEs shall be followed until the event has resolved or until study exit. In case of permanent impairment, the event shall be followed until the event stabilizes and the overall clinical outcome has been ascertained.

Reporting of AEs and DDs shall end once the subject exits the study. In any case where AEs are unresolved at the time of study exit, this shall be documented on the eCRF.

The investigator is responsible for reporting AEs to Medtronic and their local IRB (per IRB reporting requirements) as outlined in Table 7 below, by completing the Adverse Event eCRF and/or Device Deficiency eCRF. For the purposes of this CIP, planned/elective procedures for pre-existing conditions are not considered or reported as AEs as long as the pre-existing condition is not aggravated or exacerbated after a study procedure. A list of AEs that may be associated with the device and/or the interventional procedure is provided in Section 10.1.

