**Analysis Method:**

The study-related SAE rate will be summarized for the Safety population using a Kaplan-Meier curve through at least 12 months. Analyses will include survival probabilities and 95% confidence interval bands through the 12-month visit. Subjects not completing the study will be censored after their last available visit. A sensitivity analysis shall be performed where a cumulative incidence curve is estimated and death will be accounted for as a competing risk.

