- Subject chooses to withdraw (e.g., consent withdrawal, relocation to another geographic location)
- Investigator deems withdrawal necessary (e.g. medically justified, inclusion/exclusion criteria not met, failure of subject to maintain adequate study compliance)

[figure not shown]
Analysis:

Analysis can only be completed for subjects that have case report forms saved complete.

Allocation:

Since the Ellipsys post-market surveillance study is not a randomized study, all study subjects that are enrolled are allocated to the intervention (i.e. are treated with the Ellipsys Vascular Access System).

Figure 1 – Example of STROBE Flow Diagram

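### Protocol 9.16.1 and SAP 7.1.1 allow a subject in whom the device was deployed to be exited for ineligibility or poor compliance, against Protocol 9.16.5, which permits avoidable and possibly informative censoring of both 12-month primary curves

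*Protocol*

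**What the plan says.** **Exit reasons.** Protocol 9.16.1 lists situations in which a subject may be exited. One is "Subject did not meet inclusion/exclusion criteria". Another is "Investigator deems withdrawal necessary (e.g., medically justified, inclusion/exclusion criteria not met, failure of subject to maintain adequate study compliance". Not having been treated with the study device is a separate item, so the eligibility item is not confined to untreated subjects. SAP 7.1.1 carries the same list, including "Investigator deems withdrawal necessary (e.g. medically justified, inclusion/exclusion criteria not met, failure of subject to maintain adequate study compliance".

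**The competing rule.** Protocol 9.16.5 states: "No subjects should be withdrawn by investigators unless compelling medical justification is present". Protocol 9.15 lists as a deviation: "Included subject did not meet inclusion/exclusion criteria".

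**What follows exit.** Protocol 11.5: "Reporting of AEs and DDs shall end once the subject exits the study". For study-related SAEs, Protocol 13.2.2 says: "Subjects not completing the study will be censored after their last available visit". Protocol 13.2.3 and SAP 7.7.1 and 7.8.2 apply the same rule, so it governs both 12-month primary curves. The sensitivity analysis planned for each is a cumulative incidence curve with death as the competing event.

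**Analysis status.** Protocol 9.16: "Subjects who discontinue participation prior to study completion shall be included in the analysis of results but shall not be replaced". The Safety and Treated sets (Protocol 13.1, SAP 7.1.3) do not depend on eligibility.

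**The concern.** The two protocol sections give a site different instructions. Poor compliance is not in itself a medical justification, and neither is an eligibility failure found on later review. A site can exit such a subject under 9.16.1 or keep the subject under 9.16.5 and claim adherence either way.

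Once a deployed subject is exited, later study-related SAEs and access abandonment are not captured. Kaplan-Meier then treats that subject's future as if it matched the future of those still followed. If the reason for exit is related to later risk, the estimate is biased, and an analysis that handles only death does not address this.

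The study asks how the device performs with newly trained providers. Errors of patient selection by those providers are arguably part of that performance, which makes this an awkward group to lose. Discontinued subjects are also not replaced, so such exits use up the attrition allowance.

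**Working it through.** **1. Can the exit apply after deployment?** Enrolment is signature of consent (Protocol 8.2, 9.6), so a consented subject who fails a check before the procedure does need an exit code. Protocol 8.3 has imaging criteria 10 and 11 (vessel proximity and diameter) confirmed immediately before device use, so most vessel-size failures should be found before treatment. That recheck does not cover the exclusions in 8.4, such as central venous stenosis or prior ipsilateral surgery, which could come to light later. Failure to comply with the study can arise during follow-up. The route is therefore open for deployed subjects.

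**2. Does another rule restore the lost events?** Protocol 9.16 and the set definitions keep the subject in the analysis, but only with data up to exit. Protocol 11.3 asks sites to keep following unresolved events after early exit, not to collect new ones. SAP 7.1.1 tabulates exits by reason, which shows how many were lost but does not correct the curve.

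**3. The plan's own figure.** Enrolment for 100 evaluable subjects at 25% drop-out: 100/(1 - 0.25) = 133.3, rounded up to 134. This reproduces. The allowance is 134 - 100 = 34 losses.

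**4. Illustrative size.** The documents give no event rate, exit share or hazard ratio, so all of these are assumptions:
- p, 12-month risk in the other subjects: 10%, 15% or 20%
- w, share exited: 5% or 10% (about 7 or 13 of 134)
- c, time of exit: month 1 or month 3, in years
- h, hazard in exited subjects relative to the rest: 0.5, 1, 2 or 3
- constant hazards, with λ = -ln(1 - p)

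True risk = 1 - [(1 - w)e^(-λ) + w·e^(-hλ)].

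Kaplan-Meier limit = 1 - [(1 - w)e^(-λc) + w·e^(-hλc)] × e^(-λ(1 - c)).

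Worked case, p = 15%, w = 5%, c = 0.25, h = 2:
- λ = 0.1625
- True risk = 1 - (0.95 × 0.85 + 0.05 × 0.7225) = 15.64%
- Kaplan-Meier = 1 - (0.95 × 0.9602 + 0.05 × 0.9220) × 0.8852 = 15.17%
- Difference: -0.47 points

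| h | Kaplan-Meier minus true risk, over all p, w and c |
|---|---|
| 0.5 | +0.18 to +0.87 points |
| 1 | 0 |
| 2 | -0.33 to -1.45 points |
| 3 | -0.62 to -2.59 points |

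The largest gap, -2.59 points, is one corner: p = 20%, w = 10%, exit at month 1, h = 3 (20.29% estimated against 22.88% true).

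**5. Bounds without a hazard model.** Take a 15% estimate and 7 of 134 exited. If all 7 later fail, the estimate is too low by 7/134 × 0.85 = 4.4 points. If none do, it is too high by 7/134 × 0.15 = 0.8 points.

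**6. Scale.** A simple 95% half-width at 15% is 1.96 × √(0.15 × 0.85/n): 7.0 points at n = 100 and 6.0 at n = 134.

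**7. Attrition.** Seven to 13 such exits would use 7/34 = 21% to 13/34 = 38% of the allowance. This is approximate, because the 134 are consented subjects and some will never have the device deployed.

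**The case against.** The strongest reply is that the exit list is mostly administrative. Subjects enrol at consent, imaging eligibility is confirmed at the procedure, and those who fail then must be coded somehow. SAP 7.1.1 introduces its list as reasons that study exit might include, which describes disposition and does not grant permission. Protocol 9.16.1 urges subjects to stay, and 9.16.5 is the specific rule for investigator withdrawal: it recommends discussion with the study team and asks for the reason and rationale. A subject can also be both a reported deviation and an exit, so 9.15 alone adds no contradiction.

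Much of this stands, and it narrows the problem to eligibility failures found after deployment and to non-compliance. It does not close the route, because 9.16.1 offers as examples two grounds that 9.16.5 would not accept.

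Three further limits also stand:
- Protocol Table 6 attributes events to the index procedure mainly within 30 days, so that part of the SAE endpoint would largely precede an exit at month 1 to 3. The constant-hazard model therefore probably overstates the effect on SAEs, although SAEs from secondary procedures could still be missed.
- Early occlusion is assessed by day 7 with the whole Safety set as denominator (SAP 7.8.1) and is little affected.
- Removing the compliance exit does not bring back subjects who stop attending. Some will become lost to follow-up and be censored in the same way.

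**Conclusion.** The point holds as a contradiction with a consequence for the analysis. Protocol 9.16.1 and SAP 7.1.1 permit exits of deployed subjects that 9.16.5 would refuse. Those exits stop endpoint capture and lead to censoring in both 12-month primary curves, and no planned analysis covers informative censoring other than death.

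A reader might infer that the highest-risk subjects are the ones removed, and that the curves will therefore look better than they should. The documents do not support that. No section says that subjects found ineligible or non-compliant carry higher later risk. Exclusions 1 and 2 in Protocol 8.4 mention interference with the procedure or with maturation, which makes higher risk plausible for those failures. It does not show it for all such exits.

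Under the stated assumptions, Kaplan-Meier understates 12-month risk by about 0.3 to 2.6 points at two to three times the hazard, is unbiased at equal hazard, and overstates it by about 0.2 to 0.9 points at half the hazard. All of these are smaller than the sampling half-width of about 6 to 7 points at 15% risk, in a descriptive study with no hypothesis test. The case for changing the text is that the loss is avoidable and cheap to prevent. A large bias has not been shown.

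**What to change.** Reconcile Protocol 9.16.1 and SAP 7.1.1 with Protocol 9.16.5:

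1. Limit two exit reasons, unmet inclusion/exclusion criteria and not treated with the study device, to subjects in whom the Ellipsys device was never deployed.
2. Remove unmet criteria and inadequate compliance from the examples of investigator withdrawal.
3. State that a deployed subject later found ineligible is reported as a deviation and, unless consent is withdrawn, stays in follow-up to 12 months and in the analysis sets.
4. Optionally, add to the SAP a best-case/worst-case sensitivity analysis for withdrawals other than death, for the SAE and cumulative patency curves. This would also cover subjects who stop attending, whom the wording change cannot recover.

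The cost is wording in two documents and, if item 4 is adopted, one short additional analysis. The small downside is that a few ineligible or poorly compliant subjects must still be followed, at visits already in the schedule.
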